Randomization and Blinding

Patients will be randomized 1:1 to the HPTC or dHCAM group using a computer-generated randomization sequence. Due to the nature of the interventions, blinding of participants and clinicians is not feasible. However, outcome assessors and data analysts will be blinded to group assignments.

Data Collection and Monitoring

- a. Baseline data: Demographics, medical history, ulcer characteristics.
- b. Weekly follow-ups: Wound measurements (photographic documentation), assess healing progress, record adverse events and patient-reported outcomes.
- c. End-of-Study Visit (Week 5): final wound assessment, collect patient feedback on treatment experience.
- d. Data entry and monitoring will be managed using an electronic data capture system.
- e. Regular monitoring will ensure adherence to the study protocol and address any compliance issues.

Statistical Analysis

Descriptive statistics for baseline characteristics. Statistical analysis was performed using SPSS version 26.0 (IBM Corp., Armonk, NY). Continuous variables were presented as mean \pm standard deviation or median (interquartile range) based on distribution normality assessed by Kolmogorov-Smirnov test. Categorical variables were presented as frequencies and percentages.

Between-group comparisons for continuous variables were performed using independent t-test or Mann-Whitney U test as appropriate. Chi-square test or Fisher's exact test was used for categorical variables. Time-to-event analysis was performed using Kaplan-Meier survival curves with log-rank test. Repeated measures ANOVA was used to analyse wound size changes over time.

Statistical significance was set at p<0.05. All analyses were performed on intention-to-treat basis with last observation carried forward for missing data.

Sample Size Calculation

Sample size calculation was based on expected difference in wound closure rates between groups. Assuming 85% closure rate in HPTC group versus 65% in dHACM group, with 80% power and 5% significance level, 38 patients per group were required. To account for 10% dropout rate, 40 patients per group were enrolled.

Study completion

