Patients will complete the study 6 weeks after the first treatment visit. In addition, if, patients whose study ulcer closes prior to the 6-week visit will be considered as having completed the study. Complete healing of the study ulcer is defined as 100% re-epithelialization without drainage. At any point during the treatment period, patients can refuse to participate or withdraw from the study without prejudice. If a patient withdraws from the study, their last available wound measurement will be carried forward and used to calculate change in wound size and their final outcome

Ethical Considerations

- i. Approval will be obtained from the Institutional Ethics Committee.
- ii. Adherence to the Declaration of Helsinki and Good Clinical Practice (GCP) guidelines.
- iii. Informed and written consent will be obtained from all participants.
- iv. Adverse events will be monitored and reported.
- v. Participants may withdraw at any time without penalty.
- vi. Dissemination of Results
- vii. Findings will be submitted to peer-reviewed journals and presented at relevant conferences.

Timeline

Recruitment: 1 months Intervention: 3 months

Data analysis and reporting: 1 months

Potential Implications

This study aims to provide direct comparative data on the efficacy of HPTC versus dHACM in the treatment of pressure sores. The findings could inform clinical decision-making and potentially lead to improved patient outcomes in wound care management of pressure sores.

References:

- 2. Berhane, C. C., Brantley, K., Williams, S., Sutton, E., & Kappy, C. (2019). An evaluation of dehydrated human amnion/chorion membrane allografts for pressure ulcer treatment: a case series. *Journal of Wound Care*, 28(Sup5), S4–S10. https://pubmed.ncbi.nlm.nih.gov/31067170/
- 3. Vecin, N. M., & Kirsner, R. S. (2023). Skin substitutes as treatment for chronic wounds: current and future directions. *Frontiers in Medicine*, 10, 1154567. https://www.ncbi.nlm.nih.gov/pmc/articles/PMC10498286/
- 4. Helicoll® Clinical Study Publications. [https://helicoll.com/clinical-studies/]
- 5. A Randomized Controlled Clinical Trial Comparing the Use of High-Purity Type I Collagen Matrix (HPTC) and Dehydrated Human Amnion/Chorion Membrane (dHACM) Allografts in the Management of Diabetic Foot Ulcers.

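### The 10% dropout allowance assumes withdrawn patients leave the closure comparison, but the carry-forward rule keeps them in as not closed, so adding patients does not by itself preserve the stated power

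*Combined protocol and SAP*

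**What the plan says.** Three parts of the combined protocol and SAP bear on this point.

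- **Sample Size Calculation.** The basis is closure: "Sample size calculation was based on expected difference in wound closure rates between groups". The requirement reads "Assuming 85% closure rate in HPTC group versus 65% in dHACM group, with 80% power and 5% significance level, 38 patients per group were required". The next sentence is the dropout allowance: "To account for 10% dropout rate, 40 patients per group were enrolled".
- **Statistical Analysis.** The analysis set and missing-data rule are "All analyses were performed on intention-to-treat basis with last observation carried forward for missing data". For a yes/no outcome such as closure, "Chi-square test or Fisher's exact test was used for categorical variables".
- **Study completion.** For a patient who withdraws, "their last available wound measurement will be carried forward and used to calculate change in wound size and their final outcome". The same section says that "patients whose study ulcer closes prior to the 6-week visit will be considered as having completed the study".

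The plan does not say whether 85% and 65% describe patients who stay, all randomised patients with withdrawals counted as failures, or all patients under full follow-up. It also does not say whether the 5% level is one- or two-sided.

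**The concern.** Adding patients for dropout is the right remedy when dropouts are missing from the analysis: the expected rates stay the same, the number analysed falls, and extra recruitment restores it. Under this plan's rules the number analysed does not fall. Everyone randomised stays in the comparison, and those who withdraw enter with an open ulcer. What can change is the pair of closure rates being compared. The difference may shrink, and the rates move towards 50%, where a proportion is more variable.

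If so, the trial is sized for one effect and its analysis estimates another. The conflict would also outlast a correction of the 38. Recomputing the base number and inflating it in the usual way could still report 80% power that the carry-forward analysis does not have.

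**Working it through.** **Inputs.** Closure 85% (HPTC) and 65% (dHACM), 80% power, 5% level, 10% dropout and 40 per group, all from Sample Size Calculation; 1:1 allocation from Study Design. Two-sided testing is assumed; one-sided results are given where they matter.

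**1. The plan's own figures.** With p̄ the mean of p₁ and p₂, the pooled two-proportion formula is

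n = [1.960·√(2p̄(1−p̄)) + 0.842·√(p₁(1−p₁)+p₂(1−p₂))]² / (p₁−p₂)².

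For 85% vs 65%, p̄ = 0.75 and n = (1.2002 + 0.5015)² / 0.20² = 72.4, so 73 per arm. One-sided gives 57. Unpooled, arcsine and continuity-corrected variants give 55 to 83. None gives 38.

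The dropout step does not reproduce either: 38/0.9 = 42.2, so 43. Going from 38 to 40 covers 1 − 38/40 = 5%.

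**2. How a withdrawn patient is counted.** A patient whose ulcer closes early is a completer. A patient who withdraws therefore had an open ulcer at the last measurement. Carrying that measurement forward gives the outcome not closed, and intention to treat keeps the patient in the denominator.

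**3. Analysed rates.** Assume that 85% and 65% apply to patients who stay, and that 10% withdraw in each arm regardless of healing:

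- HPTC: 0.90 × 85% = 76.5%
- dHACM: 0.90 × 65% = 58.5%
- Difference: 18 points instead of 20

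**4. Power at 40 per arm.** Power = Φ{[(p₁−p₂)√n − 1.960·√(2p̄(1−p̄))] / √(p₁(1−p₁)+p₂(1−p₂))}.

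- 85% vs 65%: Φ[(0.20·√40 − 1.2002)/0.5958] = Φ(0.109) = 54.3%
- 76.5% vs 58.5%: Φ[(0.18·√40 − 1.2982)/0.6500] = Φ(−0.246) = 40.3%

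Exact enumeration of the uncorrected chi-square test gives 55.3% and 40.1%. Fisher's exact test gives 46.0% and 31.7%. One-sided power is 66.7% and 53.0%.

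**5. Splitting the shortfall (two-sided).** From 80% to 54% is 26 points, due to the base number. From 54% to 40% is 14 points, due to dilution under the step 3 assumptions.

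**6. Would correcting the base number be enough?** At 76.5% vs 58.5%, n = (1.2982 + 0.5471)² / 0.18² = 105.1, so 106 per arm. Conventional inflation of the right base number gives 73/0.9 = 81.1, so 82 per arm, where power at the diluted rates is 69.5%. These sizes only illustrate that the conflict is separate from the 38; nobody has planned them.

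**7. Range at 40 per arm, two-sided.**

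| Assumption | Analysed rates | Power |
|---|---|---|
| 85%/65% already count withdrawals as not closed | 85% vs 65% | 54% |
| 85%/65% are full-follow-up rates; those who withdraw would not have closed anyway | 85% vs 65% | 54% |
| 5% withdraw in each arm | 80.75% vs 61.75% | 47% |
| 10% in each arm | 76.5% vs 58.5% | 40% |
| 15% in each arm | 72.25% vs 55.25% | 35% |
| 20% in each arm | 68% vs 52% | 31% |
| 5% HPTC, 15% dHACM | 80.75% vs 55.25% | 69% |
| 15% HPTC, 5% dHACM | 72.25% vs 61.75% | 17% |

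As a further check, take 85% and 65% as full-follow-up rates, with withdrawal at a constant hazard that stops at closure and 10% withdrawing (in each arm or on average). The analysed rates are then about 77–79% vs 59–61%, and power is 39–47%.

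**The case against.** A reader might infer that the closure test will certainly compare 76.5% with 58.5%, or that the dropout conflict is why power is near 40%. The documents support neither.

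- **The rates are conditional.** The plan does not say what population 85% and 65% describe, or that withdrawal is equal between arms and unrelated to healing. If those who withdraw are mainly patients whose ulcers would not have closed, the analysed rates stay near 85% and 65%. This stands, and it limits the claim to a possible dilution.
- **Equal withdrawal is not the natural case.** Closers cannot withdraw, so a faster-healing arm has less time at risk, and the trial is open label. Unequal withdrawal can raise power above 54% as well as lower it. This stands: even the direction of the change is not fixed.
- **Most of the shortfall lies elsewhere.** It comes from the 38. This stands.
- **The allowance may be merely redundant.** If 85% and 65% already count withdrawals as failures, it is harmless and adds two patients per arm. That is true, but the sentence then describes an adjustment with no function.
- **Scope.** Closure is listed as a secondary outcome, and the plan also names Kaplan-Meier and log-rank methods without saying how withdrawals are treated there. The point is therefore limited to the chi-square/Fisher comparison. Closure is nevertheless the only outcome on which the trial is sized, so the stated 80% depends on it.

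None of this removes the mismatch between a sizing step that takes patients out and an analysis rule that keeps them in.

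**Conclusion.** The conflict holds on the text alone. The dropout allowance presumes losses from the closure comparison, whereas the analysis rules retain withdrawn patients as not closed. Extra enrolment therefore does not by itself preserve the stated power.

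The size of the effect depends on assumptions. Under the simplest set (rates among stayers, 10% withdrawal in each arm, unrelated to healing) two-sided power at 40 per arm is about 40%, against about 54% with all 40 analysed at 85% vs 65%. The dropout conflict thus accounts for up to about 14 points under that set, on top of the larger shortfall from the 38. Other withdrawal patterns give anything from 17% to 69%. No pattern in the table reaches 80%.

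**What to change.** Keep enrolment at the 40 per arm used in the sample size section, and restate both sample-size sentences together. Changing only the dropout sentence would leave "with 80% power and 5% significance level, 38 patients per group were required" standing beside a much lower power. (Study Design gives both 40 per arm and 20 per group; those lines need to agree with whichever number is kept.)

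First state whether 85% and 65% already count withdrawals as not closed.

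- **If they do:** delete the 10% allowance and state power of about 54% at 40 per arm, two-sided.
- **If they do not:** state that withdrawn patients are analysed as not closed and give the expected analysed rates. Replace the claim of 80% power with 38 per group by the power at 40 per arm: about 40% at 10% equal withdrawal, 47% to 31% for 5% to 20%, with the unequal-withdrawal cases alongside.

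In either case, say that the test is two-sided if that is intended. The cost is a few sentences and a less favourable stated power. No extra patients are needed, and the analysis itself does not change.

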Title: Treatment of Pressure Ulcers using Biological Skin Substitutes: A Comparison of Type-I Collagen and Amnion/Chorion Membranes

NCT: NCT06853210

Date: 26/07/2025

Background

Pressure ulcers, also known as decubitus ulcers or bedsores, are localized injuries to the skin and underlying tissue resulting from prolonged pressure. They are prevalent in individuals with limited mobility, such as the elderly and those with spinal cord injuries, particularly in long-term care settings. Effective management of pressure ulcers is crucial to prevent complications and improve patient outcomes, includes pressure relief, wound care, and advanced therapies such as bioengineered skin substitutes. Management of pressure sores is crucial due to their association with increased morbidity, healthcare costs, and reduced quality of life. This study aims to evaluate the efficacy of two treatment modalities: Type-I Collagen-based Skin Substitute (HPTC) vs. Dehydrated Human Amnion/Chorion Membrane (dHCAM) in promoting the healing of pressure ulcers. While both products are used in wound management, direct comparative studies evaluating their efficacy in treating pressure ulcers are limited.

MATERIALS AND METHODS

This prospective, randomized, controlled, open label, two parallel group, single-centre clinical trial will be conducted at a tertiary care hospital, in India, specializing in wound care and reconstructive surgery. The study protocol was approved by the Institutional Ethics Committee (Approval Number: AIMS/IEC/012/2025) and pre-registered with the ClinicalTrials.gov (NCT06853210). All procedures will be performed in accordance with the Declaration of Helsinki and Good Clinical Practice guidelines. All participants or guardians will be provided informed consent.

Outcome Measures

Primary Outcome:

- a. Percentage Wound Area Reduction.
- b. Histopathological Parameters
 - i. Vascular Infiltration
 - ii. Neo-epithelialization
 - iii. Fibroblast Activity
 - iv. Capillary Density
 - v. Inflammatory Response
 - vi. Collagen Deposition

Secondary Outcomes:

- a. Complete Wound Closure Rates (defined as 100% epithelialization).
- b. Wound Size Progression Over Time 7 weeks

- c. Number of Reapplications
- d. Incidence of treatment-related adverse events (e.g., infection, allergic reactions)
- e. Quality of Life Improvement
- f. Patient Satisfaction Scores

Study Design

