Prospective, randomized, controlled, single-centre study with two parallel-group, open-label trial Duration: 6 weeks of intervention with follow-up for 1 week. Participants will be randomly assigned in a 1:1 ratio to receive either HPTC or dHCAM treatment

Sample Size: 80 patients (40 per arm)

- i. Group A: 20 patients receiving HPTC treatment.
- ii. Group B: 20 patients receiving dHCAM treatment.

Eligibility Criteria

Inclusion criteria

- a. Subjects must be at least 18 years of age or older
- b. Presence of a Stage III or Stage IV pressure ulcer, as defined by the National Pressure Ulcer Advisory Panel
- c. Ulcer size between 5 cm² and 25 cm²
- d. Ulcer duration of at least 4 weeks prior to enrolment
- e. The subject must agree to attend the twice-weekly/weekly study visits required by the protocol
- f. The subject must be willing and able to participate in the informed consent process
- g. Adequate blood supply to the affected area, confirmed by clinical assessment

Exclusion criteria

Potential subjects meeting any of the following criteria will be excluded from enrolment.

- a. A subject known to have a life expectancy of <6 months
- b. Presence of infection in the ulcer requiring systemic antibiotics.
- c. Known allergy to components of HPTC or dHCAM.
- d. Participation in another wound care study within the last 30 days.
- e. A subject with autoimmune or connective tissue disorders.
- f. Women who are pregnant or considering becoming pregnant within the next 6 months and those who are breast feeding.
- g. History of autoimmune disease, immunosuppressive therapy, malignancy, or uncontrolled diabetes (HbA1c >10%).

Study treatment

The treatment phase will begin with a series of assessments designed to confirm the patients' continued eligibility. Subjects who continued to meet study inclusion criteria after the screening period were randomized to one of two groups:

- 1. HPTC
- 2. dHCAM

Interventions

Wound Preparation - Prior to application, wounds will be debrided to remove necrotic tissue and cleansed with a standard saline solution.

Application Protocol:

- a. HPTC Group: Participants will receive standard wound care plus application of HPTC
- b. dHCAM Group: Participants will receive standard wound care plus application of dHCAM

All participants will receive standard care measures, including:

- a. Regular repositioning to alleviate pressure.
- b. Nutritional support to address deficiencies.
- c. Management of comorbid conditions.

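### A patient counts as having completed the study once the ulcer closes: no confirmation visit is specified, nothing provides for assessment or adverse-event recording afterwards, and the end of study is placed at weeks 5, 6 and 7

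*Combined protocol and SAP*

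**What the plan says.** All references are to the combined protocol and SAP.

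- **Study completion.** "Patients will complete the study 6 weeks after the first treatment visit". For those who heal sooner, "patients whose study ulcer closes prior to the 6-week visit will be considered as having completed the study". The definition is "Complete healing of the study ulcer is defined as 100% re-epithelialization without drainage". It sets no duration and no repeat visit. The definition of closure under Outcome Measures (secondary outcome a) sets none either.
- **Study Design.** "Duration: 6 weeks of intervention with follow-up for 1 week", which makes 7 weeks.
- **Outcome Measures.** Secondary outcome b is "Wound Size Progression Over Time 7 weeks". Secondary outcome d is "Incidence of treatment-related adverse events", with no reference to time observed.
- **Data Collection and Monitoring.** Wound measurements and adverse events are recorded at weekly follow-ups. The last visit is "End-of-Study Visit (Week 5): final wound assessment, collect patient feedback on treatment experience".
- **Statistical Analysis.** Categorical outcomes are compared by chi-square or Fisher's exact test, wound size over time by repeated measures ANOVA, and missing values are filled by last observation carried forward (LOCF).

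No section says whether visits or adverse-event recording go on after closure.

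**The concern.** The rule makes the length of observation depend on the outcome. If a patient's visits end when the ulcer is first read as closed, three things follow.

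1. That single reading settles the closure outcome. LOCF then carries an area of zero through the remaining weeks, which feeds percentage area reduction (a primary outcome), the closure rate on which the trial was sized, and the repeated measures analysis of wound size.
2. A wound that reopens is not recorded, so a difference in durability between the two products could not be detected.
3. Patients who heal sooner contribute fewer weeks in which an adverse event can be seen. A comparison of crude proportions then leans towards the faster-healing arm even when the weekly risk is the same.

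Fewer weeks on treatment may be a genuine benefit of a product. Fewer weeks of observation are not.

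There is also a plain contradiction about when the study ends, and it affects every patient, not only those who heal early.

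**Working it through.** **Inputs from the plan.** 40 per group and closure of 85% (HPTC) and 65% (dHCAM), both from Sample Size Calculation; weekly visits; 6 weeks of intervention plus 1 of follow-up. The plan gives no time point for the 85% and 65%, no reopening rate and no adverse-event rate, and it has no figure of its own on this point to reproduce. Everything below that needs those quantities is an assumption.

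**Step 1. The stated end of study.**

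| Section | End of observation |
|---|---|
| Data Collection and Monitoring | week 5 |
| Study completion | week 6, or earlier at closure |
| Study Design | 6 + 1 = week 7 |
| Outcome Measures, secondary b | week 7 |

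These cannot all hold. Read literally, the 6-week completion rule leaves no week-7 data for anyone, whether closed or not.

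**Step 2. How many patients might complete early.** Closures at the planned rates: 0.85 × 40 + 0.65 × 40 = 34 + 26 = 60 of 80 (75%). If the rates refer to week 6, this is an upper bound.

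- Closures spread evenly over weeks 2 to 6: four fifths occur before week 6, so 0.8 × 60 = 48 of 80 (60%).
- Weibull time to closure with shape k, fixed to 85% and 65% at week 6: share closed by week 5 = 1 − (1 − p)^((5/6)^k). Averaged over the arms, this is 69% for k = 1, 62% for k = 2, 56% for k = 3, about 50% for k = 4 and 44% for k = 5.

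**Step 3. Reopening.** With an assumed reopening share r, equal in both arms, the difference in lasting closure is (0.85 − 0.65)(1 − r).

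- r = 5%: 0.20 × 0.95 = 19 points.
- r = 15%: 0.20 × 0.85 = 17 points.

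**Step 4. Adverse events.** Assume that closures spread evenly over weeks 2 to 6, that observation stops at closure if this is before week 6 and otherwise runs to week 7, and that the weekly risk is a constant h. The chance of at least one event in T weeks is 1 − (1 − h)^T.

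Mean time for closers: (2 + 3 + 4 + 5 + 7)/5 = 4.2 weeks.

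- HPTC: 0.85 × 4.2 + 0.15 × 7 = 4.6 weeks.
- dHCAM: 0.65 × 4.2 + 0.35 × 7 = 5.2 weeks.

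At h = 5%, the chances for T = 2, 3, 4, 5, 7 are 9.75%, 14.26%, 18.55%, 22.62% and 30.17%, with mean 19.07%.

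- HPTC: 0.85 × 19.07% + 0.15 × 30.17% = 20.7%.
- dHCAM: 0.65 × 19.07% + 0.35 × 30.17% = 23.0%.
- Gap: 0.20 × (30.17% − 19.07%) = 2.2 points.
- Full follow-up to week 7: 30.2% in both arms.

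| Assumed weekly risk | HPTC | dHCAM | Gap (points) | Full 7 weeks, both arms |
|---|---|---|---|---|
| 2% | 8.8% | 9.9% | 1.0 | 13.2% |
| 5% | 20.7% | 23.0% | 2.2 | 30.2% |
| 10% | 37.3% | 40.8% | 3.5 | 52.2% |

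If observation ends at week 6 for the rest, as Study completion says, the 5% row becomes 19.6% against 21.2%, a gap of 1.6 points, with 26.5% in both arms under full observation to week 6.

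**The case against.** The strongest reply is that the text never says visits stop. Such patients are only considered to have completed; the plan has a one-week follow-up, and adverse events are to be monitored with no stated stop at closure. That stands as far as it goes: the documents leave the rule unstated. But ending at completion is the natural reading, and the silence itself needs repair.

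Second, first closure is a legitimate event, and the plan includes a Kaplan-Meier and log-rank analysis. Asking for lasting closure is partly a choice of endpoint. This also stands, and it is a reason to report both.

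Third, treatment-related events such as infection or allergic reaction may be less likely once the ulcer has closed. A lower risk after closure would shrink both the gap and the under-counting in Step 4.

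A reader might go further than the documents allow in four ways:

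- *That closure is never verified.* Outcome assessors are blinded, wounds are photographed, and absence of drainage is required. What is missing is a repeat visit.
- *That early closure leaves most patients without week-7 data.* The early share is 44% to 69% over the time courses tried and 75% at most, so a majority is not assured. The literal 6-week completion rule comes first and removes week 7 for all.
- *That unequal reopening distorts the treatment difference by a large amount.* No source in the documents supports any reopening rate, still less a difference between arms.
- *That HPTC is the arm favoured.* It is the faster-healing arm only under the planning assumption.

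**Conclusion.** The concern holds as a gap in the rules for observation. Completion is tied to the outcome, no confirmation visit is specified, and nothing provides for assessment or adverse-event recording after closure. If visits do end at closure, reopening is hidden and adverse-event time is shorter in whichever arm heals sooner.

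The between-arm adverse-event bias is modest: about 2 points on the assumptions of Step 4, and 1.0 to 3.5 points for weekly risks of 2% to 10%. The larger effect is under-counting in both arms, roughly 7 to 9.5 points at 5% a week (30.2% against 23.0% and 20.7%). The effect of reopening on the closure difference cannot be known from the documents; the 19 to 17 points are illustrative only.

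The conflict between weeks 5, 6 and 7 rests on no assumption and must be reconciled in any case. The change should be made: it is cheap, and it removes outcome-dependent follow-up.

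**What to change.** 1. Reconcile the end of study to one time point in all sections. Week 7 matches the stated follow-up and the wound-size outcome.
2. Keep every randomised patient in the weekly assessments to that point, whatever the closure status. This concerns assessment only and says nothing about treatment after closure.
3. Count closure as confirmed when it is first seen by week 6 and still present at the next weekly visit. The week-6 cutoff is needed because a closure first seen at week 7 has no later visit. Report first closure as well.
4. Collect adverse events to week 7 in everyone, and report events per patient-week beside the crude incidence.

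The cost is a few extra short visits for early closers, on the existing weekly schedule, and a reported closure rate that may be slightly lower. Patients who close early will still be watched for reopening longer than those who close late (five weeks after a week-2 closure, one after a week-6 closure). The confirmation rule uses the same one-week window for all, so the confirmed-closure outcome is not affected by this.
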